5 TREATMENT PLAN

This is an open-label Phase I trial evaluating the combination of pazopanib, an oral VEGFR inhibitor, and ARQ 197, an oral MET inhibitor, in patients with refractory advanced solid tumors. Reported adverse events and potential risks for pazopanib and ARQ 197 are described in [Section 7](#). Appropriate dose modifications for pazopanib and ARQ 197 are described in [Section 6](#). No investigational or commercial agents or therapies other than pazopanib and ARQ 197 may be administered with the intent to treat the patient's malignancy.

The study will be carried out in 2 phases, as described in [Section 5.1](#). The drugs will be administered in 28-day cycles (\pm 1 day for scheduling). Pazopanib tablets should be administered orally without food (at least 1 hour before or 2 hours after eating) once a day. ARQ 197 tablets should be administered orally with food twice daily approximately every 12 hours. A missed or vomited dose should not be replaced. The patient should be instructed to take the next scheduled dose at the regularly scheduled time. Patients will be asked to maintain a Study Medication Diary ([Appendix E](#)) and record each dose of medication. Patients will be given instructions for completing the medication diary and will be asked to return it to the clinic staff at the end of each cycle.

With Amendment H, dated 09/26/2013: For patients who have been on study for six or more cycles and are tolerating treatment well, two months worth of drug may be dispensed at a time; labs and blood pressure monitoring will only be performed once every 2 cycles (every 2 months). More frequent labs and assessment can be performed as clinically indicated.

History and physical examination can be done up to 3 days before start of a new cycle. Patients will be examined on D1, D8 (only for patients who will have tumor biopsy), and D15 in the dose escalation phase, or D1 and D8 in the expansion phase, at the clinical center for the first cycle and prior to every new cycle. Blood pressure (BP) will be checked every 2 weeks during the first 2 cycles in the dose escalation phase and on D1 and D8 of cycle 1 in the expansion phase, and then at the beginning of subsequent cycles. Mid-cycle blood pressure monitoring can be performed by any healthcare provider.

Labs (CBC with differential; serum chemistries, including glucose) will be performed as follows:

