5.2.1 Grade \geq 3 Non-Hematological Toxicity

Grade \geq 3 non-hematological toxicity felt to be related to study medications will be considered dose-limiting with the following clarifications:

- 5.2.1.1 Diarrhea Grade 3 will only be considered dose-limiting if it is refractory to treatment as outlined in [Section 5.3.2](#), Supportive Care Guidelines, and unable to be corrected to Grade 2 or less within 24 hours. Bloody or Grade 4 diarrhea will be dose-limiting.
- 5.2.1.2 Nausea and vomiting Grade 3 will only be considered dose-limiting if it is refractory to anti-emetic therapy and unable to be corrected to Grade 1 or less within 24 hours ([Section 5.3.1](#)).
- 5.2.1.3 Rise in creatinine to Grade 3, not corrected to Grade 1 or less within 48 hours with IV fluids will be considered dose-limiting. All Grade 4 rises in creatinine will be dose limiting.

5.2.1.4 Grade ≥ 3 metabolic toxicities unable to be corrected to Grade 2 or less within 48 hours (such as glucose changes, hypocalcemia or hypercalcemia, hypomagnesemia or hypermagnesemia, hyperuricemia, hypophosphatemia, and hyponatremia) will be considered dose limiting. For hypokalemia or hyperkalemia, grade ≥ 2 toxicities unable to be corrected to grade 1 or less within 48 hours will be considered dose limiting. Grade 4 metabolic toxicities that are symptomatic will be considered dose-limiting regardless of duration or ability to correct.

5.2.1.5 QTc prolongation to ≥ 500 msec on at least two separate EKGs (refer to [Section 5.3](#)) will be dose limiting.

5.2.1.6 AST/ALT > 8 X ULN or AST/ALT > 3 X ULN and concurrent bilirubin elevation > 2 X ULN will be dose limiting.

5.2.1.7 Grade ≥ 3 bleeding in any sites or grade ≥ 2 pulmonary bleeding will be dose limiting.

5.2.1.8 Grade 4 venous thrombosis, pulmonary embolism, or any grade of arterial thrombosis will be dose limiting.

5.2.2 Grade 4 thrombocytopenia.

5.2.3 Grade 4 neutropenia ≥ 3 days or febrile neutropenia.

5.2.4 Any degree of anemia, leucopenia in the absence of grade 4 neutropenia ≥ 3 days, or lymphopenia will not be considered dose limiting.

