5.3 General Concomitant Medication and Supportive Care Guidelines

All patients will be provided with the best available supportive care. All concurrent medications should be documented prior to initiation of treatment, and be periodically reviewed with the patient. Particular attention must be paid to medications which may prolong the QTc interval ([Appendix C](#)) and agents that interact with CYP450 isoenzymes ([Appendix B](#)).

QTc Prolongation:

Caution should be exercised when administering pazopanib to patients with a history of QTc interval prolongation, in patients taking anti-arrhythmics or other medications that may prolong the QTc interval, and those with relevant pre-existing cardiac disease. A list of medications that may cause QTc interval prolongation are listed in [Appendix C](#), and should be avoided by patients on this study. EKG will be performed as described in [Section 5](#). If the QTc interval on follow-up EKG is ≥ 500 msec, the EKG should be repeated within 7 days and, if the QTc interval remains ≥ 500 msec, the subject should be removed from the study. Additionally, if the QTc interval is increased by 60 msec or more from baseline but the QTc interval remains at <500 msec, the EKG should be repeated within 7 days. If the repeat EKG again shows a ≥ 60 msec increase in the QTc interval from baseline, consideration should be given to removing

the subject from the study or increasing monitoring, after discussion with the principal investigator.

CYP450 Interactions:

In vitro and in vivo animal data indicate that the metabolism of pazopanib is primarily mediated by CYP3A4. In vitro data indicate that pazopanib is a potential inhibitor for CYP2C9, CYP1A2, CYP2A6, CYP2B6, CYP2C8, CYP2C19, CYP2D6, CYP2E1, and CYP3A4. In addition, one in vitro study suggested that pazopanib may induce CYP3A4 at high concentrations. Potent CYP3A4 inhibitors and inducers are prohibited on pazopanib trials. In exceptional circumstances, medications which strongly inhibit CYP3A4 may be administered, with caution, if the dose of pazopanib is decreased to 50% of the dose which would otherwise be administered.

Medications that strongly inhibit CYP3A4 include (but are not limited to):

- Antibiotics: clarithromycin, telithromycin, troleandomycin
- HIV: protease inhibitors (ritonavir, indinavir, saquinavir, nelfinavir, amprenavir, lopinavir)
- Antifungals: itraconazole, ketoconazole, voriconazole
- Antidepressant: nefazodone

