6 DOSING DELAYS/DOSE MODIFICATIONS

Toxicities (hematologic and non-hematologic; except any grade lymphopenia, anemia, or alopecia) should have resolved to \leq Grade 2 prior to starting the next cycle or receiving the next dose of pazopanib or ARQ 197 within a cycle. Study drugs should be held for hypokalemia or hyperkalemia \geq grade 2; hypocalcemia or hypercalcemia \geq grade 3; hypophosphatemia \geq grade 3; hypomagnesemia or hypermagnesemia \geq grade 3. These laboratory values should be corrected as soon as possible in a manner consistent with good medical judgment. Study drugs may be re-administered when hypokalemia or hyperkalemia is grade 1 or within institutional limits; hypocalcemia or hypercalcemia is \leq grade 2; hypophosphatemia is \leq grade 2; and hypomagnesemia or hypermagnesemia is \leq grade 2. Even though study drug administration is allowed at these lower grades, every effort should be made to correct the abnormal lab values to normal if possible. If the potassium level is grade 2 or greater and/or if the calcium, magnesium, and/or phosphate are grade 3 or higher, an EKG must be performed and appropriate action taken based on the results.

Treatment may be delayed for a maximum of 2 weeks for toxicities. In case toxicities do not resolve as stated, the patient will not receive further therapy on this protocol and will be followed for resolution of toxicities. Start of next cycle may be delayed for up to 1 week to accommodate scheduling conflicts. Dose modifications are intended for within-cycle and start-of-next-cycle changes. If administration of study drug is interrupted for any reason, it will not be made up, and

counting of the cycle days continues (i.e., if a patient stops pazopanib and ARQ 197 on day 15 and resumes 2 days later, they will be considered day 17).

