6.1.7 Cardiac Toxicity

1. Discontinue pazopanib in patients who develop symptomatic heart failure.
2. Modify the pazopanib dose using the table presented in [Appendix F](#) in patients who develop compromised symptomatic LVEF. The NCI developed the table in [Appendix F](#) using the NSABP-B31 and NCCTG9831 monitoring guidelines for adjuvant trastuzumab in patients with breast cancer. These studies enrolled populations considered most likely to be cured; thus, the investigators used the most stringent and conservative monitoring.
3. Discontinue ARQ 197 in patients who develop symptomatic bradycardia.

4. Patients with asymptomatic bradycardia will not have drug held or dose modified. Bradycardic patients with a heart rate ≤ 50 beats per minute should have an EKG done on day 1 of every cycle, or as clinically indicated.
5. QTc Prolongation, see Table 6.

Table 6: Management of QTc Prolongation

If EKG reveals an increase in the QTc to ≥ 500 msec or an increase in the QTc by at least 60 msec from baseline	Repeat EKG before re-administration of pazopanib and/or ARQ 197
If repeat EKG shows QTc interval is ≥ 500 msec	Remove subject from study
If on repeat EKG, QTc remains at least 60 msec longer than baseline but is less than 500 msec	Consider removing subject from study

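### For the same QTc result, Section 5.3 allows 7 days to the repeat EKG and states no hold, while Table 6 wants the repeat before re-dosing and sets no interval; one hold-and-repeat rule is needed.

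*Combined protocol and SAP*

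**What the plan says.** Three places deal with a prolonged QTc on study.

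- **Section 5.2.1.5 (DLT definition).** A QTc at or above "500 msec on at least two separate EKGs" is dose limiting. The only cross-reference is to Section 5.3.
- **Section 5.3 (concomitant medication and supportive care).** At 500 msec or more, "the EKG should be repeated within 7 days and, if the QTc interval remains" at that level, the subject leaves the study. A rise of 60 msec or more that stays below 500 msec has the same 7-day window. If the repeat confirms that rise, removal or closer monitoring is considered. The paragraph does not mention holding either drug and does not point to Table 6.
- **Section 6.1.7, item 5.** It reads "QTc Prolongation, see Table 6". Table 6 has the same two triggers and the instruction "Repeat EKG before re-administration of pazopanib and/or ARQ 197". It gives no number of days. Removal at a repeat of 500 msec or more matches Section 5.3.

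Some general text also bears on the question. Section 5 says "Appropriate dose modifications for pazopanib and ARQ 197 are described in" Section 6. Section 6 asks that toxicities be no worse than "Grade 2 prior to starting the next cycle or receiving the next dose of pazopanib or ARQ 197 within a cycle", and adds "Treatment may be delayed for a maximum of 2 weeks for toxicities" and "If administration of study drug is interrupted for any reason, it will not be made up". Section 5.1.1 counts a patient without DLT in the escalation decision only if at least 80% of the planned cycle 1 doses were taken.

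**The concern.** No single section tells the clinician both whether to keep dosing and how soon to repeat the EKG while a possible DLT is pending. Someone who starts from the DLT rule is sent to Section 5.3 and finds a week's allowance with no hold. Someone who starts from Table 6 finds an implied hold with no deadline of its own, and *and/or* leaves open whether one drug may resume first. Other rules in Section 6 are explicit. Section 6.1.3 holds both drugs for Grade 3 neutropenia or thrombocytopenia, and the hypertension, proteinuria and liver tables say outright to hold or interrupt pazopanib.

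Safety is the main stake. Section 2.2 reports Torsades de Pointes in pazopanib trials. Section 7.1.2 lists QTc prolongation for ARQ 197 with the relationship undetermined. Sinus bradycardia is listed for both agents, and Appendix C treats bradycardia as a Torsades risk factor.

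The second stake is DLT ascertainment in the 3+3. Escalation EKGs are planned at baseline, C1D1 and C1D15, and otherwise as clinically indicated. After a prolongation first seen on C1D15, the repeat therefore supplies the second EKG that the DLT needs. One DLT separates escalating (0 of 3) from adding patients (1 of 3).

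**Working it through.** The plan states no figure on this point, so there is none to reproduce. The check compares the texts and then counts doses.

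**1. Side by side**

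| | Section 5.3 | Table 6 |
|---|---|---|
| Triggers | 500 msec or more; rise of 60 msec or more | same |
| Dosing until the repeat | not stated | no re-administration before the repeat; which drug is unclear |
| Time to the repeat | within 7 days | not stated (general 2-week cap in Section 6) |
| Repeat at 500 msec or more | remove | remove |
| Cited by 5.2.1.5 | yes | no |

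Hold plus repeat by day 7 meets both columns. If Section 5.3 were read alone and dosing went on for the full week, the patient could take up to 7 pazopanib doses and 7 × 2 = 14 ARQ 197 doses at the BID levels before the repeat.

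**2. Effect of a hold on cycle 1 evaluability**

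Inputs: 28 pazopanib doses and 56 ARQ 197 doses per cycle at the BID levels; 80% threshold (Section 5.1.1); missed doses not made up (Section 6).

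Needed: 0.8 × 28 = 22.4, so 23 pazopanib doses; 0.8 × 56 = 44.8, so 45 ARQ 197 doses.

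| Days missed | Pazopanib | ARQ 197 | Share | Evaluable without DLT |
|---|---|---|---|---|
| 1 | 27/28 | 54/56 | 96.4% | yes |
| 2 | 26/28 | 52/56 | 92.9% | yes |
| 5 | 23/28 | 46/56 | 82.1% | yes |
| 6 | 22/28 | 44/56 | 78.6% | no |
| 7 | 21/28 | 42/56 | 75.0% | no |

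If the evening ARQ 197 dose on the day of the first EKG is also withheld, a 5-day hold leaves 56 − 10 − 1 = 45 doses (45/56 = 80.4%), which still passes. The 7-day window therefore permits holds on either side of the threshold. Five missed days is the most that a patient can afford, counting any missed for other reasons.

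**3. Pazopanib left at the repeat**

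Inputs from Section 2.2: mean half-life 30.9 h in the 800 mg once-daily group; geometric means from 18.1 to 52.3 h. Assumption: first-order decline, so fraction left = 2^(−t / half-life).

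| Time since last dose | 18.1 h | 30.9 h | 52.3 h |
|---|---|---|---|
| 24 h | 39.9% | 58.4% | 72.8% |
| 48 h | 15.9% | 34.1% | 52.9% |
| 144 h | 0.4% | 4.0% | 14.8% |
| 168 h | 0.2% | 2.3% | 10.8% |

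This shows how much drug remains, not how far QTc recovers. The documents give no concentration-QTc relationship, and the calculation leaves out ARQ 197.

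**4. How many patients**

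Section 7.1.1 lists QTc prolongation for pazopanib as rare (under 3%). Section 13.2 caps escalation at 36 patients. If that rate held for the combination, the expected number is under 0.03 × 36 = 1.08. The listing is not restricted to 500 msec or to cycle 1, which would lower the count. It is also a single-agent rate, and the combination could be higher. Section 3.2.6 excludes a baseline QTc of 480 msec or more.

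**The case against.** The best defence is that the protocol already contains a complete rule in two compatible halves. Section 5.3 concerns supportive care, Section 5 sends dose modifications to Section 6, and Section 6.1.7 sends QTc to Table 6. Silence in 5.3 does not authorise dosing that Table 6 bars. With daily and twice-daily drugs, repeating before re-administration most naturally means before the next dose, and 7 days is a ceiling. This stands, and it rules out the stronger inference that the sections contradict each other or that the protocol as a whole permits dosing at 500 msec. It does not remove the risk for a reader who follows the DLT rule to the one section it cites.

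A second defence is that the general Section 6 rule on resolution to Grade 2 already forces a hold. That depends on how a first QTc of 500 msec is graded under CTCAE, which the documents do not reproduce, so the rule cannot be relied on here.

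Third, the evaluability and washout effects come from the length of the 7-day window, and aligning the sections would not by itself cure them. That is right, and it is why the remedy needs a prompt repeat as well as a cross-reference. A reader might also infer that a long hold records a false absence of DLT. The documents do not support that for a 6- or 7-day hold: such a patient is not evaluable and is left out of the cohort decision. Nor do continued exposure and washout arise together, since they follow from opposite readings.

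Fourth, any hold means the confirming EKG is taken during some washout. This stands: at the mean half-life about 42% to 66% of pazopanib is gone at 24 to 48 h. A prompt repeat reduces the problem without removing it.

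**Conclusion.** The point holds as a misalignment with a safety risk for a reader of Section 5.3 alone. For one EKG result, one section gives a deadline without a hold, another gives an implied hold without a deadline, and the DLT rule cites only the first. This is a cheap improvement to make, not a flaw that undermines the design.

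The effect on DLT assessment is secondary and limited to escalation cycle 1. Holds of 6 or 7 days make a patient without DLT non-evaluable; 5 days or fewer do not. About one patient of 36 or fewer would meet the event, on the assumption that the single-agent listing carries over, and only some of those would be held 6 days or longer. That a late repeat may miss a drug-related prolongation is plausible from the half-life under first-order decline, but without concentration-QTc data it remains a possibility.

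**What to change.** Put the same rule in Section 5.3 and Table 6. At a QTc of 500 msec or more, or a rise of 60 msec or more from baseline, hold both pazopanib and ARQ 197 until the EKG has been repeated, and repeat it promptly, ideally before the next scheduled dose. The sponsor should set an outer limit short enough to keep a cycle 1 patient evaluable, meaning no more than 5 missed days in total. An interval of 24 to 48 h is only an example and has no source in the documents. Replace *and/or* in Table 6 with wording that names both drugs. Have 5.2.1.5 cite Table 6 as well as Section 5.3. Leave the two-EKG DLT criterion and the removal rules as they are.

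The repeat EKG is already required, so the cost is an earlier unscheduled visit, including for rises of 60 msec or more that stay below 500 msec, and a dose or two of each drug that is not made up. A hold of 1 to 2 days keeps the patient well within the 80% rule.

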6.1.8 Management of Subjects with Elevations in AST, ALT and/or Bilirubin

Table 7: Management of Liver Function Test Abnormality

AST, ALT and/or Bilirubin	
Isolated AST/ALT elevations between 3X ULN and 8X ULN	Continue pazopanib, but monitor weekly until AST/ALT returns to ≤ 2.5 or baseline
AST/ALT > 8 X ULN	Hold pazopanib until AST/ALT returns to ≤ 2.5 X ULN or baseline. If the potential benefit of reinitiating pazopanib treatment is considered to outweigh the risk for hepatotoxicity, then consider reintroducing pazopanib at a reduced dose of 400 mg once daily and measure serum liver tests weekly for 8 weeks only after discussion with the PI and CTEP. If AST/ALT elevations > 3 X ULN recur, then pazopanib should be permanently discontinued.
AST/ALT > 3 X ULN and concurrent bilirubin elevations > 2 X ULN	Permanently discontinue pazopanib.
Mild indirect hyperbilirubinemia, known or suspected Gilbert's syndrome, and elevation in ALT > 3 X ULN	Continue pazopanib, but monitor weekly until ALT returns to grade 1 (NCI CTCAE) or baseline.

6.1.9 Reversible Posterior Leukoencephalopathy Syndrome (RPLS) or similar leukoencephalopathy syndrome

RPLS or clinical syndromes related to vasogenic edema of the white matter have been rarely reported in association with pazopanib therapy ($< 3\%$). Clinical presentations are variable and may include altered mental status, seizure, and cortical visual deficit.

Hypertension is a common risk factor in patients who develop RPLS. MRI scans are key to diagnosis and typically demonstrate vasogenic edema (hyperintensity in T2 and FLAIR images and hypointensity in T1 images) predominantly in the white matter of the posterior parietal and occipital lobes; less frequently, the anterior distributions and the

gray matter may also be involved. RPLS should be in the differential diagnosis in patients presenting with unexplained mental status changes, visual disturbance, seizure or other CNS findings. RPLS is potentially reversible, but timely correction of the underlying causes, including control of blood pressure and interruption of the offending drug, is important in order to prevent progression to irreversible tissue damage. Pazopanib should be held in patients with symptoms/signs suggestive of RPLS, pending work-up and management, including control of blood pressure. Pazopanib should be discontinued upon diagnosis of RPLS.

After consultation with the study PI and CTEP, NCI, consideration of restarting the study drugs may be evaluated in light of any clinical benefit.

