5.1 Agent Administration

5.1.1 Dose Escalation Phase

A primary objective of the trial is to establish the safety, tolerability, and MTD of the combination. Pazopanib will be administered QD, starting at 400 mg, and ARQ 197 will be administered BID, starting at 120 mg (dose level 1). The duration of a cycle will be 28 days (\pm 1 day for scheduling). Dose escalation will proceed in cohorts of 3 patients each (3+3 design) as outlined below (Table 2):

Table 2: Dose Escalation Scheme

Dose Level	Pazopanib	ARQ 197
-2	200 mg QD	120 mg QD
-1	400 mg QD	120 mg QD
1 (starting dose)	400 mg QD	120 mg BID
2	600 mg QD	120 mg BID
3	600 mg QD	240 mg BID
4	800 mg QD	240 mg BID
5	800 mg QD	360 mg BID
6*	600 mg QD	360 mg BID

*If dose level 5 is above the MTD, dose level 6 will be evaluated.

Tumor biopsies will be optional during the escalation phase. For the escalation phase, 3 patients should have completed at least one cycle of therapy prior to considering dose escalation in the next cohort of patients. Dose escalation will proceed according to the following scheme. DLT is defined in [Section 5.2](#). Determination of DLT will be based on toxicities observed in the first cycle of therapy. Patients are considered evaluable for toxicity for the purpose of cohort dose escalation decisions if they either 1) experienced DLT or 2) have received at least 80% of the planned 28-day doses of treatment in one cycle of therapy and have been followed for one full cycle without DLT. All toxicities will be reported for all patients who receive any amount of study drug on this study. Evaluation of toxicity will begin with study drug administration on cycle 1 day 1.

Number of Patients with DLT at a Given Dose Level	Escalation Decision Rule
0 out of 3	Enter 3 patients at the next dose level.
≥ 2	Dose escalation will be stopped. This dose level will be declared the maximally administered dose (highest dose administered). Three (3) additional patients will be entered at the next lowest dose level if only 3 patients were treated previously at that dose.
1 out of 3	Enter at least 3 more patients at this dose level. 
 • If 0 of these 3 patients experience DLT, proceed to the next dose level. • If 1 or more of this group suffer DLT, then dose escalation is stopped, and this dose is declared the maximally administered dose. Three (3) additional patients will be entered at the next lowest dose level if only 3 patients were treated previously at that dose.

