5.4 Duration of Therapy

In the absence of treatment delays due to adverse events, treatment may continue until one of the following criteria applies:

- Disease progression
- Intercurrent illness that prevents further administration of treatment

- Significant toxicity occurs despite 2 dose reductions as described in [Section 6](#) or no lower dose level exists
- Pregnancy
- Patient decides to withdraw from the study, or
- General or specific changes in the patient's condition render the patient unacceptable for further treatment in the judgment of the investigator.

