A maximum of 2 dose reductions will be allowed before patient is taken off treatment. Patients who require a dose reduction will not have the dose re-escalated. Dose reductions may occur to a single compound independent of the other compound if toxicity necessitating a dose reduction is attributed to a single agent in the opinion of the study Principal Investigator. One dose level reduction due to pazopanib-associated toxicities such as hypertension means that pazopanib dose should be reduced to 400 mg if an original dose is 600 mg or to 600 mg if it is 800 mg. Similarly, one dose level reduction due to ARQ 197-associated toxicities means that ARQ 197 dose should be reduced to 120 mg bid if an original dose is 240 mg bid, or to 240 mg bid if it is 360 mg bid.

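### Table 7's fixed 400 mg re-challenge dose after AST/ALT above 8 times ULN is no reduction for patients already on 400 mg

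*Combined protocol and SAP*

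**What the plan says.** Table 7 in Section 6.1.8 deals with AST/ALT above 8 times ULN by holding pazopanib until the values return to 2.5 times ULN or baseline. If benefit is then judged to outweigh the liver risk, the investigator may "consider reintroducing pazopanib at a reduced dose of 400 mg once daily". This needs prior discussion with the PI and CTEP and weekly liver tests for 8 weeks. Pazopanib stops for good if AST/ALT rises above 3 times ULN again. The 400 mg figure carries no condition on the current dose.

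Other relevant text:

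- Section 5.1.1: "Pazopanib will be administered QD, starting at 400 mg". Table 2 gives 400 mg at levels 1 and -1, 600 mg at levels 2, 3 and 6, 800 mg at levels 4 and 5, and 200 mg at level -2.
- Section 5.2.1.6: "AST/ALT > 8 X ULN or AST/ALT > 3 X ULN and concurrent bilirubin elevation > 2 X ULN will be dose limiting".
- Section 6: "A maximum of 2 dose reductions will be allowed before patient is taken off treatment", with no re-escalation after a reduction. On step sizes, "pazopanib dose should be reduced to 400 mg if an original dose is 600 mg or to 600 mg if it is 800 mg". No step below 400 mg is named there.
- Section 6 also limits interruptions: "Treatment may be delayed for a maximum of 2 weeks for toxicities".
- Section 5.4 ends treatment if "Significant toxicity occurs despite 2 dose reductions" or if "no lower dose level exists".
- Table 5 (proteinuria, Section 6.1.6) uses a relative rule, 200 mg off the current dose, and stops pazopanib when no further cut is possible.

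**The concern.** A fixed number works as a reduced dose only if every patient to whom it applies was on more than that number. Here the number equals the starting dose of the trial. For a patient on 400 mg, the word 'reduced' and the figure of 400 mg cannot both be obeyed, and the figure is the part a clinician can act on. Followed literally, it returns the patient to the dose on which a dose-limiting liver event occurred.

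This is a patient-safety point about dosing instructions. The protocol treats liver injury as a serious risk: Section 2.2 reports deaths with hepatic failure in 2 of 977 patients in the renal cell trials and 1 of 240 in the sarcoma trial, and Section 5 sets out a liver-monitoring plan. Sample size, the 3+3 rules and the biomarker analysis are not involved.

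**Working it through.** **1. Size of the reduction, by current dose.** Change = (400 − current dose) / current dose, using the doses in Table 2.

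| Current pazopanib dose | Calculation | Change under Table 7 |
|---|---|---|
| 800 mg | (400 − 800)/800 | −50% |
| 600 mg | (400 − 600)/600 | −33% |
| 400 mg | (400 − 400)/400 | 0% |
| 200 mg | (400 − 200)/200 | +100% |

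The last row would also breach the ban on re-escalation in Section 6 for anyone who had been reduced to 200 mg.

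**2. Who can be on 400 mg with a reduction still available.** Count one reduction as one 200 mg pazopanib level, as Section 6 does. Reductions used to reach 400 mg = (assigned dose − 400)/200.

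| Dose levels | Assigned dose | Reductions used at 400 mg | Further reduction allowed (maximum 2)? |
|---|---|---|---|
| 1, −1 | 400 mg | 0 | Yes |
| 2, 3, 6 | 600 mg | 1 | Yes |
| 4, 5 | 800 mg | 2 | No |
| −2 | 200 mg | not applicable | not applicable |

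So the gap can arise in 5 of the 8 rows of Table 2. Only level 1 is certain to enrol patients directly at 400 mg. Level −1 opens only on de-escalation, level 6 only if level 5 exceeds the MTD, and at levels 2, 3 and 6 an earlier reduction must already have been made. Patients brought from 800 mg to 400 mg by two toxicity reductions are already directed off treatment by Sections 5.4 and 6.

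**3. Whether another section supplies the missing dose.**

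- Section 6.1.1 requires modification for grade 3 or higher non-hematologic toxicity and does not exempt transaminases, but it gives no dose.
- Section 6 names steps from 800 to 600 mg and from 600 to 400 mg only.
- Section 5.4 stops patients for whom no lower level exists. Level −2 contains 200 mg pazopanib, so it does not clearly stop a patient on 400 mg.
- Table 5 uses a 200 mg step, but only for proteinuria.

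**4. How often it might matter.** The protocol gives no rate for AST/ALT above 8 times ULN. Assume 1% to 10% per patient, and 3 to 6 evaluable patients at level 1.

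- Expected events: 3 × 0.01 = 0.03, up to 6 × 0.10 = 0.6.
- Chance of at least one: 1 − 0.99³ = 0.030, up to 1 − 0.90⁶ = 0.469.

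These count liver events. Re-challenges would be fewer, because the patient must also recover within the 2-week limit and be approved for re-challenge.

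**The case against.** The strongest reply is that Table 7 never orders an unreduced restart. It permits consideration of a reduced dose; where 400 mg is not a reduction, the permission does not fit and the hold stands. Section 6.1.1 points the same way, since restarting 400 mg after 400 mg modifies nothing. The PI and CTEP would discuss each case and would probably notice. This reading is reasonable and lowers the risk, but it has to be inferred. The only dose in the row is 400 mg, the general sections are not cross-referenced to it, and the discussion does not change the written dose.

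A second reply is that the scope looks larger than it is. That is fair: five rows of Table 2 are not five populated cohorts, and the 10% rate has no source in the protocol. The timed figures in Section 2.2 are for the lower threshold of ALT above 3 times ULN, 1% at week 2 and about 5% at week 3. The 47% is best read as an upper bound under an assumption.

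A third reply concerns strong CYP3A4 inhibitors, with which Sections 3.2.5 and 5.3 exceptionally allow pazopanib to be halved. An 800 mg patient could then be on 400 mg with no toxicity reduction used, so the entry for levels 4 and 5 above has that rare exception. It enlarges the affected group slightly, and the proposed rule would send such a patient to 200 mg. Halving 600 mg gives 300 mg, which cannot be made from unbroken 200 mg and 400 mg tablets (Section 8.1), so that case does not undermine the rule.

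Finally, whether 200 mg is worth giving after such an event, or whether stopping is better, is a clinical choice. That stands; either answer would close the gap if written down.

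**Conclusion.** The concern holds, at low priority. Table 7 states a single re-challenge dose that is a true reduction from 800 mg and 600 mg, no reduction from 400 mg, and an increase from 200 mg. Because 400 mg is the starting dose, the affected group is part of the design from the first cohort.

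The practical effect is small. Re-challenge is discretionary and surrounded by real safeguards, and under the assumed 1% to 10% rate level 1 would see fewer than one qualifying liver event. The conclusion on dose rests only on Table 2, Table 7 and the reduction steps in Section 6; the assumed rate bears only on how often the gap would matter.

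**What to change.** Reword the row of Table 7 for AST/ALT above 8 times ULN so that any re-challenge is at 400 mg once daily or at 200 mg below the current dose, whichever is lower. Add that pazopanib is permanently discontinued if the patient is already on 200 mg or has already had two dose reductions.

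The rule is min(400, current dose − 200): 800 mg goes to 400 mg and 600 mg to 400 mg, both as now; 400 mg goes to 200 mg; and 200 mg means stop. Keep every existing condition: recovery within the 2-week delay limit, the benefit-risk judgement, discussion with the PI and CTEP, weekly liver tests for 8 weeks, and permanent discontinuation on recurrence above 3 times ULN. If the investigators prefer not to re-challenge at 200 mg, stating that patients on 400 mg or less discontinue pazopanib would also resolve it.

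The cost is one line of protocol text. The 200 mg tablet is already supplied (Section 8.1), 200 mg is already a dose in Table 2, and a 200 mg step is already used in Table 5.
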